1. SUMMARY

1.1. SYNOPSIS

	Evaluation of the Safety and Clinical Efficacy of AZVUDINE in
TITLE	patients infected with SARS-CoV-2 virus: a Phase III,
	randomized, double-blind, PLACEBO-controlled study.
STUDY ID	IGZ-1
DOCUMENT TYPE	Phase III Clinical Trial Design
VERSION/ISSUANCE DATE	Version 0.5 of May 30, 2022
	HRH HOLDINGS LIMITED, [name]
SPONSOR	[name]
	[name].
	INSTITUTO GALZU DE PESQUISA, ENSINO, CIÊNCIA E
	TECNOLOGIA APLICADA, CNPJ: 28.831.817/0001-20.
	Office: [name], Zip Code:
REPRESENTATIVE	[name], Campos dos Goytacazes-RJ.
ORGANIZATION OF	Interface Hospitalar: [name],
CLINICAL RESEARCH	[name], Hospital Santa Casa de
SPONSOR IN BRAZIL (ORPC)	Misericórdia de Campos, [contact] Ext.
	180/194
	Contact [name] [name]
	Site: http://www.institutogalzu.org.br
	E-mail: [contact]
CTUDY CITE	Santa Casa de Misericórdia de Campos, Campos dos
STUDY SITE	Goytacazes - RJ

	Primary Goal
OBJECTIVE	 To evaluate the efficacy and safety of AZVUDINE (FNC) versus placebo in patients infected with moderate to severe stage SARS-COV-2; Secondary objective
	 To evaluate the clinical outcome between the AZVUDINE (FNC) group versus the PLACEBO group in patients infected with moderate to severe stage SARS- COV-2;
INTERVENTION	 Experimental group: AZVUDINE 5mg/day, orally for up to 14 days + Standard treatment. Control group: PLACEBO orally for up to 14 days + Standard treatment.
NUMBER OF PARTICIPANTS	Following initial study data, the sample size calculation was revised updating parameters of frequency of clinical improvement and dropout rate. The revised sample size is 180 participants randomly and equally divided into the two arms of the study (90 practitioners in each group).

The study consists of 3 periods: **screening, treatment, and follow-up.** In the screening period, patients who meet the eligibility criteria will be enrolled in the study and randomized into one of the two study arms, experimental or control. The first day of treatment will be day 1, and will last up to 14 days.

STUDY DESIGN

Treatment will be terminated early when two consecutive RT-PCR tests are negative (one of the criteria for hospital discharge). Treatment will also be stopped early in the event of participant dropout or in the event of an EAG.

	Safety follow-up will be performed at 28 and 60 days after				
	discharge. For the Early Termination (ET) of treatment, participants should follow the routine from visit 17: End of Treatment (D15), in advance. The study will be considered completed when the last				
	participant completes his or her last visit.				
	Individuals with the following characteristics will be				
	included in this study:				
	Age ≥18 years, regardless of gender;				
	2. Patients hospitalized in moderate to severe stages in				
	line with the Ministry of Health classification ¹ ;				
	3. Positive diagnostic test for SARS-CoV-2 by molecular				
INCLUSION CRITERIA	amplification of the virus in RT-PCR diagnosed from				
	respiratory specimen (nasopharyngeal, oropharyngeal,				
	lower respiratory tract [e.g., sputum]) collected <96				
	hours before randomization;				
	4. Time between symptom onset and inclusion ≤14 days;				
	5. Hospitalization within 48 hours of study inclusion;				
	6. Availability for follow-up during the study period;				

Mild: Flu-like syndrome (cough, sore throat or runny nose), followed or not by: Anosmia (olfactory dysfunction) Ageusia (gustatory dysfunction), Runny nose, Diarrhea, Abdominal pain, Fever, Chills, Myalgia, Fatigue, Headache;

Moderate: Persistent cough + daily persistent fever or Persistent cough + progressive worsening of another symptom related to COVID-19 (adynamia, prostration, hyporexia, diarrhea) or at least one of the above symptoms + presence of a risk factor.

Severe: Severe acute respiratory syndrome - influenza syndrome presenting: Dyspnea/respiratory distress or persistent chest pressure or $_{02}$ saturation less than 95% on room air or bluish coloration of lips or face.

 $^{^{\}mathrm{1}}$ The Brazilian Ministry of Health classifies the symptoms of COVID-19 into:

	7. Voluntary adherence to participate in the study and				
	signing the Informed Consent Form.				
	Individuals with one or more of the following characteristics				
	will not be eligible to participate in this study:				
	1. Patients known or suspected to be sensitive to				
	AZVUDINE or excipients (inactive ingredients:				
	microcrystalline cellulose, hydrated lactose,				
	polyvinylpyrrolidone K30, croscarmellose sodium,				
	magnesium stearate);				
	2. Patients diagnosed with pneumonia caused by other				
	pathogens;				
	3. Patients with liver disease (total bilirubin ≥2mg/dL,				
	ALT/TGP and AST/TGO ≥5 times above normal limit); ²				
EXCLUSION CRITERIA	4. Total neutrophil count <750 cells/L;				
	5. Patients with renal insufficiency (glomerular filtration				
	rate ≤60mL/min/1.73m2) or are receiving continuous				
	renal replacement therapy, hemodialysis or peritoneal				
	dialysis;				
	6. Patients with congestive heart failure (NYHA grade 3/4),				
	untreated symptomatic arrhythmias, or myocardial				
	infarction within 6 months;				
	7. Patients with a history of known liver disease (cirrhosis				
	with ChildPugh classification B and C);				
	8. Individuals with malabsorption syndrome, or other				
	conditions that affect gastrointestinal absorption, and				

² Normal values: BT up to 1.2 mg/dL; TGO Adult 12 to 46 U/L; TGP Adult 03 to 50 U/L; GGT Man 10 to 50 U/L, Woman 07 to 32 U/L (Source: Hermes Pardini Institute).

- circumstances in which patients need intravenous nutrition, or cannot take medications orally or nasogastrically;
- Women who are pregnant or lactating, or of childbearing potential during the study period and within 6 months after termination of administration;
- 10. Patients already included in other clinical trials;
- 11. Patient under treatment for HIV, Hepatitis C, active Hepatitis B;
- Patients being treated with other antivirals (e.g. lopinavir/ritronavir, remdesivir, umifenovir/arbidol, favipiravir, interferon-α)
- Patients being treated with monoclonal antibodies (e.g. tocilizumab and sarilumab/kevzara);
- 14. Patients who are on a clinical treatment plan that includes concomitant administration of any other experimental treatment or off-label use of already marketed drugs (e.g. hydroxychloroquine sulfate);
- Patients requiring invasive mechanical ventilation or extracorporeal membrane oxygenation (ECMO) at the time of randomization;
- 16. Any clinically significant medical condition or medical history that, in the investigator's opinion, may discourage participation in the study, such as corrected QT interval >480 on the electrocardiogram, among other conditions.

	The following criteria define study termination for the			
	participant:			
	1) Voluntary withdrawal from the participant at any			
	time and without any prejudice to his/her health;			
	2) Any situation, at the discretion of the Principal			
	Investigator, that puts the safety of the participant at			
	risk;			
	3) Refusal or inability to perform and/or complete			
STUDY INTERRUPTION CRITERIA	imaging and laboratory tests, when applicable;			
	4) Loss of contact with the participant for follow-up;			
	5) Death;			
	6) Hospital discharge (2 negative RT-PCR tests).			
	The following criteria define the interruption of thestudy			
	as a whole:			
	1) Termination of the trial by the sponsor, if justified;			
	2) Termination of the study by the Principal			
	Investigator, if justified;			
	3) Termination of the study at the request of local			
	ethical and health authorities.			
	Demographic data collection, physical examination, vital			
	signs assessment, blood sampling, respiratory tract			
PROCEDURES	sampling, imaging, ECG, and pregnancy testing (female			
	participants) will be performed			
OUTCOME/ENDPOINTS	PRIMARY ENDPOINT			

- Proportion of participants with clinical status improvement [Period: until D15, approximately 14 days].
 - The criterion for a participant to have an improvement in clinical status is a decrease on the WHO Clinical Improvement Ordinal Scale in at least one category compared to screening (WHO, Jun/2020).

SECONDARY ENDPOINT

- Proportion of participants with a clinical outcome of cure during the study; [Period: until D15, D21, and D28, approximately 14-30 days].
 - The clinical endpoint of cure is defined in this protocol as the absence of viral RNA in collected samples and clinical conditions for hospital discharge³.
- Time to normalization of body temperature (below 37.6°C axillary); [Period: until D15, D21 and D28, approximately 14-30 days]
- Time to improvement of diarrhea, myalgia, fatigue, malaise, cough, dyspnea, and headache; [Period: until D15, D21, and D28, approximately 14-30 days].

³ According to the WHO Working Group on Characterization and Clinical Management of COVID-19 Infection (July, 2020), clinical and virological absence of infection (non-detectable RT-PCR) is suggestive of CURE for initially infected participants.

- Changes in liver and kidney function baselines, and inflammatory and immunological markers: [Period: until D15, D21 and D28, approximately 14-30 days]
 - Lab tests performed on days D1, D3, D5, D7,
 D9, D13, D15, D21, D28, and D60.
- Evaluation of the time to negative conversion of the SARS-CoV-2 viral load by RT-PCR between AZVUDINE (FNC) group and control group; [Period: until D15, D21 and D28, approximately 14-30 days].
- Evaluation of the number of cycles for the detection of SARS-CoV-2 viral load by RT-PCR and application of the standard curve for viral load calculation; [Period: until D15, D21 and D28, approximately 14-30 days].
- Analysis of the relationship between the calculated viral load and the clinical progress of participants in the AZVUDINE (FNC) group compared to the control group; [Period: until D15, D21 and D28, approximately 14-30 days].
- Time and proportion of lung imaging improvement during treatment (Pattern of ground-glass opacities, mosaic paving, alveolar consolidation, reticular pattern/septal thickening, opacity with inverted halo, pleural/pericardial effusion, fibrosis and/or lymphadenomegaly); [Period: until D15, D21 and D28, approximately 14-30 days].
- Time of improvement and proportion of respiratory symptoms and signs during treatment (Lung rales,

- cough, sputum, sore throat); [Period: until D15, D21, and D28, approximately 14-30 days].
- Time to normalization of O2 saturation (above 95%);
 [Period: until D15, D21 and D28, approximately 14-30 days].
- Time to normalization of respiratory rate to levels ≤ 24rpm, in room air; [Period: until D15, D21 and D28, approximately 14-30 days]
- Frequency of supplemental oxygenation or noninvasive ventilation; [Period: until D15, D21 and D28, approximately 14-30 days].
- Frequency of invasive mechanical ventilation or extracorporeal membrane oxygenation (ECMO); [Period: until D15, D21 and D28, approximately 14-30 days].
- Proportion of moderate cases that progressed to severe cases requiring intensive care unit (ICU) care; [Period: until D15, D21, and D28, approximately 14-30 days].
- Length of hospital stay; [Period: until D15, D21, and D28, approximately 14-30 days].
- Occurrence of drug interactions; [Period: until D15, D21 and D28, approximately 14-30 days].
- Frequency and intensity of adverse events; [Period: until D15, D21 and D28, approximately 14-30 days].

	 Frequency and intensity of unexpected adverse events; [Period: until D15, D21 and D28, approximately 14-30 days]. Frequency and intensity of serious adverse events; [Period: until D15, D21 and D28, approximately 14-30 days]. All-cause mortality rate during the study; [Period: until D15, D21 and D28, approximately 14-30 days]. Evaluate the tolerability of AZVUDINE (FNC) use at 			
	5mg/day regimen for up to 14 days: [Period: until D15,			
	approximately 14 days].			
	 Calculating treatment adherence; 			
	 Total time of use of AZVUDINE (FNC); 			
	 Proportion of participants who withdrew 			
	consent;			
	 Proportion of participants who dropped out 			
	of treatment.			
	All statistical tests are performed by two-sided test. A			
ANALYSES	significance level of 5% will be adopted. Detailed statistical			
	methods will be provided in chapter 11.			
	From the approval of the study by the Research Ethics			
LENGTH OF STUDY	Committee and ANVISA, it is estimated to take			
	approximately 7 months to complete.			

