7. EVALUATIONS AND VISITATION SCHEDULE

Participants will preferably be evaluated by the same evaluator at the beginning of the study (screening and randomization: D-1 and D0 respectively).

During follow-up, including the assessment of participants who were not discharged after the end of treatment (D21) and at two visits after discharge: two weeks (D28) and sixty days (D60) after the end of treatment.

Table 39 shows the tests to be used to assess eligibility criteria and to monitor safety and efficacy during the study period.

The coronavirus viral load will be detected every 2 days. The treatment will

last a maximum of 14 days, and can be stopped early if two consecutive negative RT-PCR tests are obtained, or if the participant decides not to continue in the study.

During the course of treatment, if the results of safety and efficacy testing show changes of concern, the investigators must determine whether or not the participant should continue with treatment. The Principal Investigator may adjust the procedures performed during the hospital stay according to the research participant's condition and the results of clinical examinations. The schedule of study procedures and examinations is detailed in Table 9.

ltem	Requirements and outcome measures
Demographic Information	Nationality, age, sex, height and weight
Anamnesis	Past/current medical history (history of illness, history of operation), history of anaphylaxis, medication use, alcohol use, drug abuse, participation in clinical trials, surgical treatment, or pregnancy/lactation.
Vital signs	Body temperature, heart rate, respiration, blood pressure
DIGITAL OXIMETRY	-
Blood glucose	Blood glucose level
Detection of viral load by RT- PCR	Sample of airway epithelium
ECG	12-lead or 18-lead ECG
CT of the lung	-
CBC	RBC, Hb, HCT, MCV, MCH, MCHC, WBC, NEUT #, LYMPH #, MONO #, EOS #, BASO #, PLT
Biochemical Examinations	AST, ALP, Cholinesterases, ALT, Alb, TP, TBIL, DBIL, GGT, Creatinine, UREA, UA, K ⁺ , Na ⁺ , Cl ⁻ , Lactate, Ca ⁺ , P.
Taxa de sedimentação de eritrócitos (ESR)	ESR
C-reactive protein (CRP)	-

Cardiac markers and enzymes	Troponin I, BNP, CK, CK-MB
Septicemia	РСТ
Blood Lactic Acid	Lactic Acid
Interleukin-6	IL-6
Coagulation test	TP, TTPA, FIB, TT
Immunological markers	IgA, IgG, IgM, complement C3 and C4
Infectious Diseases	Ab Hepatitis A, Ag Hepatitis B, Ab Hepatitis C, Ab HIV, AbTreponema pallidum

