Respiratory parasites	Legionella pneumophila, Mycoplasma pneumoniae, Coxiella burnetii (Q-Rickettsia), Chlamydia pneumoniae, adenoviruses, respiratory syncytial virus, influenza A virus, influenza B virus, Parainfluenza virus.
Triple rapid test for respiratory parasites	Respiratory syncytial virus, adenovirus, Mycoplasma pneumoniae
T-lymphocyte subsets	CD4+ and CD8+ T-cell count
Pregnancy Test	Applicable to female participants

Table 9: Parameters for safety and efficacy evaluation

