Week/Day	D-1	D0	D1	D2	D3	D4	D5	D6	D7	D8	D9	D10	D11	D12	D13	D14	D15 after the start of treatment	D21 ⁵ after the start of treatment	D28 after start of treatment	D60 after the start of treatment ³
Visit	1	2	3	4	5	6	7	8	9	10	11	12	13	14	15	16	17	18	19	20
Interval of the visit	± 4 days	-	-	-	-	-	-	-	-	-	-	1	1	1	-	-	Antes da alta hospitalar	± 3 dias	± 3 dias	± 3 dias
STAGES	TREAT	RANDOMIZATION							BLINDI	ED TRE	ATMEN	NT¹					END OF TREATMENT ²		FOLLOW-UP	
TCLE	Х																			
DEMOGRAPHIC INFORMATION	Х																			
ANAMNESIS	Х																			
ELIGIBILITY CRITERIA	Х																			
RANDOMIZATION		X																		
DISPENSING OF THE MEDICATION		Х																		
MEDICATION ACCOUNTING		X																		
SYMPTOM MONITORING	Х					•	•			Χ		•	•	•	•	•	X	X	Х	X
VITAL SIGNS	Х		X									Χ	Χ	X	X					
FINGER OXYGEN PULSE	Х		X									Х	X	Х	Х					
BLOOD GLUCOSE			X										Х	X	Х	Х				
PREGNANCY EXAM ⁴	Х																X			X

IGZ-1

AZVUDINE Clinical Trial Design

CT LUNG		Х		Χ				Χ				Χ				X	X	X	
ECG		Χ										Χ				Χ	X	X	
RT-PCR	Х	Х		Χ		Χ		Χ		Χ		Χ		Χ		Χ	X	X	
BIOCHEMICAL EXAMINATIONS	Х	Х		Χ		Χ		Х		Χ		Χ		Х		Χ	X	Х	
T-LYMPHOCYTES		Χ		Χ		Χ		Χ		Χ		Χ		Χ		Χ	X	X	
СВС		Χ		Χ		Χ		Χ		Χ		Χ		Χ		Χ	X	X	
FUNCTION OF COAGULATION		Х														Χ	X	X	
ESR/VHS		Χ						Χ								Χ	X	X	
CARDIAC MARKERS AND ENZYMES		Х						Х								X	Х	Х	
C-REACTIVE PROTEIN		Χ						Χ								Χ	X	X	
PROCALCITONIN		Х						Х								Χ	X	Х	
IL-6		Χ						Χ								Χ	X	X	
PHOSPHORUS IN URINE		Χ														Χ	X	X	
IMMUNOLOGICAL MARKERS		Х															Х	Х	
INFECTIOUS DISEASES		Χ																	
RESPIRATORY PARASITES		Х																	
TRIPLE TEST FOR RESPIRATORY PARASITES		Х															Х	Х	
AZVUDINE OR PLACEBO ADMINISTRATION			X																

IGZ-1

AZVUDINE Clinical Trial Design

MONITORING DRUG INTERACTIONS		X	X		
AE MONITORING		X	X		

Tabela 10: Cronograma de visitas e procedimentos do estudo.

¹ Day 1 of administration will be recorded as day 1 (D1) and the treatment days follow until day 14 (D14). The Principal Investigator may adjust the procedures performed during treatment according to the condition of the research participant and the results of clinical examinations (the condition manifests itself more rapidly in some patients and these patients should be observed closely).

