² The examinations and procedures under visit 17 (D15) must be performed by all participants as soon as the treatment is terminated, including participants who have stopped treatment early (AT) and for any other reason.

³ The. procedures and examinations planned to be performed at visit D28 and D60 will be determined by the Principal Investigator according to the participants' previous examinations.

⁴ For women of childbearing age only.

⁵ Visit 18 procedures will be performed only on research participants who are still hospitalized.

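### Table 10 omits the end-of-treatment draw for the immunoglobulin and complement panel, although the secondary endpoint names D15 and lists laboratory tests on that day

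*Protocol*

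**What the plan says.** The endpoint appears in the Synopsis (1.1), Section 4, Section 7.1.2 and the methods table of Section 11.3: "Changes in liver and kidney function baselines, and inflammatory and immunological markers: [Period: until D15, D21 and D28, approximately 14-30 days". A line below it begins "Lab tests performed on days D1, D3, D5, D7" and goes on to D9, D13, D15, D21, D28 and D60. Section 11.3 assigns the endpoint a Student's t-test or Mann-Whitney test.

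Table 9 (Section 7) defines the immunological markers item as "IgA, IgG, IgM, complement C3 and C4". T-lymphocyte subsets ("CD4+ and CD8+ T-cell count"), IL-6 and CRP are separate items there.

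Table 10 (Section 7.3) has a row headed "IMMUNOLOGICAL MARKERS" with three marks: D1, D21 and D28. Its footnotes govern who is sampled:

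- Footnote 2: "The examinations and procedures under visit 17 (D15) must be performed by all participants as soon as the treatment is terminated".
- Footnote 5: "Visit 18 procedures will be performed only on research participants who are still hospitalized".
- Footnote 3: "procedures and examinations planned to be performed at visit D28 and D60 will be determined by the Principal Investigator", according to earlier results.

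**The concern.** The endpoint text and the schedule of procedures disagree about when one panel is drawn, and sites work from the schedule. If the site follows Table 10, nobody has an immunoglobulin or complement value between D1 and the end of treatment, and the comparison promised for D15 has no data for these analytes.

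What remains is weaker. The D21 value exists only for participants not yet discharged. Two negative RT-PCR tests are among the discharge criteria, and time to RT-PCR negativity is itself an outcome the drug is meant to change. Treatment may therefore affect who is in the D21 group. An analysis plan cannot repair this later, because it cannot analyse samples that were never scheduled.

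**Working it through.** No sample-size, power or alpha figure is involved, so the check compares the endpoint's list of days with the marks in Table 10.

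**Step 1: days the endpoint lists.** After D1: D3, D5, D7, D9, D13, D15, D21, D28 and D60, which is nine days. The period statement names three of them: D15, D21 and D28.

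**Step 2: reading Table 10.** The laboratory rows have 19 cells for 20 visits. This fits the loss of the D0 column when the PDF was read, leaving D-1, D1 to D14, D15, D21, D28 and D60. Two rows test that mapping. RT-PCR falls on D-1, D1, every second day to D13, then D15, D21 and D28. ECG falls on D1, D11, D15, D21 and D28. Both agree with the visit text in Section 7.3 (swabs every 48 hours; ECG on D1 and D11 during treatment, and again at D15, D21 and D28).

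**Step 3: marks per row.**

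| Row in Table 10 | D1 | D2 to D14 | D15 | D21 | D28 | D60 |
|---|---|---|---|---|---|---|
| Immunological markers | yes | none | **no** | yes | yes | no |
| Coagulation | yes | none | yes | yes | yes | no |
| CRP, IL-6, ESR, procalcitonin | yes | D7 | yes | yes | yes | no |
| T-lymphocytes | yes | D3, D5, D7, D9, D11, D13 | yes | yes | yes | no |
| Biochemistry (also D-1) | yes | D3, D5, D7, D9, D11, D13 | yes | yes | yes | no |

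**Step 4: comparison.** The immunological row has 2 post-baseline marks against 9 listed days, so 9 - 2 = 7 listed days have no draw (D3, D5, D7, D9, D13, D15, D60). The core result does not depend on column counting: two post-baseline marks cannot cover the three named times, however they are aligned. Other rows also depart from the list. CRP, IL-6, ESR and procalcitonin have 4 of the 9 listed days. Biochemistry is marked on D11, which the list omits, and not on D60, which the list includes.

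**Step 5: who contributes at each time.**

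- D15 (visit 17): all participants, at end of treatment or early termination. Section 7.3 includes blood collection at this visit, but the panel is not marked.
- D21 (visit 18): only participants still in hospital. The number per arm is 90 times the share still in hospital. The documents give no such share, so it could be anything from 0 to 90.
- D28 (visit 19): marked in Table 10, and Section 5.1.1 says blood is taken on D28. However, the visit 19 procedure list has no blood sample collection beyond glucose measurement, and footnote 3 leaves the D28 examinations to the investigator.

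For this panel, then, no post-baseline time is both marked in Table 10 and assured for all participants.

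**The case against.** The strongest reply is that the endpoint text itself orders tests on D15 and that visit 17 takes blood from everyone for efficacy and safety monitoring. On this view the empty D15 cell is a missed mark, and nothing says that Table 10 overrides the endpoint. This stands in part. A reader might infer that the on-treatment change cannot be measured at all; the documents support only a contradiction, with that consequence if Table 10 is the version followed.

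Second, a reader might infer that the whole immunological or inflammatory endpoint is lost. It is not. CD4+ and CD8+ counts and all four inflammatory markers are marked at D15 and at least once during treatment, and liver and kidney tests follow the 48-hour pattern. The problem is five analytes within one composite secondary endpoint.

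Third, a reader might infer that the D21 values come from the sickest participants and that the comparison is confounded by severity. The documents do not show this. Because discharge also depends on RT-PCR, the D21 group may include people who have recovered clinically but remain positive. What stands is that the group is selected after randomisation. That applies to every D21 test, but for this panel D21 is also the first value after baseline.

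Fourth, the three-time period is attached to most secondary endpoints, and Section 11.3 names no separate D21 test for these markers. That is true, but it does not supply the missing D15 data.

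**Conclusion.** The point holds as an internal contradiction with a practical consequence. The endpoint names D15 and lists that day for laboratory tests, while Table 10 gives the IgA, IgG, IgM, C3 and C4 panel no draw between D1 and D21. If Table 10 is followed, the end-of-treatment comparison for these five analytes has no data, the D21 comparison rests on a post-randomisation subset of unknown size, and D28 is not assured.

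This rests on Table 9's definition of the panel and on the count of marks in a table read from PDF, which two other rows corroborate. The matter is minor: it concerns part of one secondary endpoint and leaves the primary endpoint, the sample size and the other markers untouched.

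**What to change.** 1. Mark the immunological panel at visit 17 (D15 or end of treatment) in Table 10 and make that the between-arm comparison for these analytes. Record the study day of the draw, because visit 17 is brought forward when treatment ends early and so is not a fixed day 15.
2. Report the D21 values of this panel descriptively only.
3. Align the endpoint's list of days with Table 10 wherever it appears (Sections 1.1, 4, 7.1.2 and 11.3): settle D11 and D60, and state which panels are drawn on which days.
4. Do not restrict this part of the endpoint to D28 unless that draw is made firm in both the visit 19 procedure list and footnote 3.

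The cost is one assay panel on a blood sample that visit 17 already takes, plus wording changes. No extra visit or blood draw is needed.
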